### **9.2.5      Unexpected AE or Unexpected Suspected Adverse Reaction**

An AE or suspected adverse reaction is considered “unexpected” if it is not listed in the Reference Safety Information in the Investigator’s Brochure or is not listed at the specificity or severity that has been previously observed.

For example, under this definition, hepatic necrosis would be unexpected (by virtue of greater severity) if the Investigator’s Brochure referred only to elevated hepatic enzymes or hepatitis. Similarly, cerebral thromboembolism and cerebral vasculitis would be unexpected (by virtue of greater specificity) if the Investigator’s Brochure listed only cerebral vascular accidents.

“Unexpected,” as used in this definition, also refers to AEs or suspected adverse reactions that are mentioned in the Investigator’s Brochure as occurring with a class of drugs or as anticipated from the pharmacological properties of the drug but are not specifically mentioned as occurring with the particular drug under investigation.

## **9.3      Adverse Event Classification**

### **9.3.1      Relationship to Investigational Product**

The Investigator’s assessment of causality must be provided for all adverse events (serious and non-serious). An Investigator’s causality assessment is the determination of whether there exists a reasonable possibility that the investigational product caused or contributed to an AE.

- Not related: The AE is clearly not related or is unlikely to be related to the study therapy. The temporal relationship of the onset of the AE relative to administration of the product is not reasonable, or the AE can be explained by another cause such as an underlying

medical condition or other concomitant medication, or the adverse event has no plausible relationship to study therapy.

- Related: The AE is related to the study therapy. The temporal relationship of the AE to administration of the product is reasonable and there is no other cause to explain the event. AEs should be classified as related if the investigator feels there is evidence to suggest a causal relationship between the drug and the adverse event.

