### **3.2 Endpoints**

#### **3.2.1 Safety Endpoints**

- The safety and tolerability of MRG-201 will be assessed by determining the incidence and severity of clinically significant adverse events (including Grade 3 and 4 AEs, treatment-related AEs, SAEs, and AEs requiring discontinuation of MRG-201), and physical examination findings, changes in vital signs, electrocardiograms (ECGs), and laboratory parameters.
- AEs will be assessed according to the National Cancer Institute (NCI) Common Terminology Criteria for Adverse Events (CTCAE), version 5.0.

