#### **9.2.2 Suspected Adverse Reaction**

A suspected adverse reaction is any AE for which there is a reasonable possibility that the drug caused the AE. For the purposes of Investigational New Drug (IND) safety reporting, “reasonable possibility” means there is evidence to suggest a causal relationship between the drug and the AE. Suspected adverse reaction implies a lesser degree of certainty about causality than adverse reaction, which means any AE caused by a drug.

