### **11.4.3 Analysis of the Safety Endpoint: Safety and Tolerability**

#### ***11.4.3.1 Adverse Events***

The analysis of the safety endpoint will be based on AE incidence, physical examination findings, vital signs, ECG results and changes in clinical laboratory tests.

Adverse events will be coded by preferred term and system organ class using the Medical Dictionary for Regulatory Activities (MedDRA®) and summary tables for all AEs will be

generated for the FAS. Incidence rates and percentages will be summarized for each preferred term and system organ class. Additional summary tables will be generated for the following subsets: subjects with SAEs, subjects with related AEs, subjects with severe (Grade 3 or 4) AEs, and subjects who discontinue due to AEs. Depending on the doses achieved in this study, AEs may also be summarized by dose level. Severity, investigator-attributed relationship to study treatment, and action taken will also be recorded.

Concomitant medications will be coded using the World Health Organization Drug Dictionary (WHO-DD; 01 September 2017 or later version). A dictionary listing of all unique concomitant medications used in the study will be provided.

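### Section 9.3.1 gives conflicting tests for an adverse event that has both evidence of drug causality and another possible explanation

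*Combined protocol and SAP*

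**What the plan says.** Section 9.3.1 opens by defining the causality assessment as a determination of "whether there exists a reasonable possibility that the investigational product caused or contributed to an AE". It then offers two grades.

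- **Not related** begins: "The AE is clearly not related or is unlikely to be related to the study therapy". It then lists three alternatives joined by 'or': unreasonable timing, that "the AE can be explained by another cause", or no plausible relationship to the therapy.
- **Related** contains this sentence: "The temporal relationship of the AE to administration of the product is reasonable and there is no other cause to explain the event". The sentence after it reads: "AEs should be classified as related if the investigator feels there is evidence to suggest a causal relationship between the drug and the adverse event".

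Section 9.2.2, on suspected adverse reactions, says that a reasonable possibility "means there is evidence to suggest a causal relationship between the drug and the AE". That gloss is given for IND safety reporting.

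The grade is used in three places. Section 3.2.1 defines the safety endpoint as clinically significant AEs, "including Grade 3 and 4 AEs, treatment-related AEs, SAEs, and AEs requiring discontinuation of MRG-201". Section 11.4.3.1 plans additional summary tables for subsets that include "subjects with SAEs, subjects with related AEs, subjects with severe (Grade 3 or 4) AEs". Section 9.4.2 requires related AEs to be followed until they resolve or stabilise, and footnote i of Appendix A repeats this in similar terms.

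**The concern.** Two neighbouring sentences of one definition set different thresholds. One is met only if nothing else explains the event. The other is met once the evidence suggests causality, and it says nothing about other causes. An investigator who applies the first literally could grade an AE to which the drug contributed as Not related. A colleague at another of the roughly four centres, applying the second, would grade the same event Related.

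Competing explanations are easy to find in this trial. Each site is a sutured punch wound that is injected four times on every dosing day (4.1, 4.2), so the biopsy, the suture and the needle are all candidate causes of local redness or swelling. Section 2.3.1 itself describes the Phase 1 injection-site reactions both as linked to the injection procedure and as drug-related.

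For systemic events, every subject receives both MRG-201 and placebo (6.2.2). There is no placebo-only group to compare with, so the investigator's causality call carries more weight. The call is made at the site, and the analysis cannot repair it afterwards.

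**Working it through.** This is a check of wording; no arithmetic applies, and the plan gives no figure to reproduce.

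Inputs, all from 9.3.1:

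- **Test A** (first quoted sentence of Related): reasonable timing AND no other explanatory cause.
- **Test B** (last sentence of Related): evidence suggesting a causal relationship is enough.
- **Test N** (Not related): any one of its three alternatives, including another explanatory cause.
- **Lead-in**: a reasonable possibility of causation or contribution.

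Assume reasonable timing and read each clause literally:

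| Evidence of drug causality | Another explanatory cause | Test A | Test B | Test N, alternative-cause clause | Result |
|---|---|---|---|---|---|
| Yes | No | Met | Related | Not triggered | Consistent: Related |
| No | Yes | Not met | Not triggered | Not related | Consistent: Not related |
| No | No | Met | Silent | Not triggered | No opposing instruction from B |
| Yes | Yes | Not met | Related | Not related | **Conflict** |

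The conflict is confined to the last row. There the lead-in sides with B, because a drug can contribute to an event only if something else may also have played a part.

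**Which clause is out of line.** Three parts of 9.3.1 lean to the inclusive test: the lead-in, the last sentence of Related (the one phrased as an instruction), and the opening of Not related, which reserves that grade for events clearly or probably unrelated. Section 9.2.2 uses nearly the same words as test B. Its gloss serves IND safety reporting and assigns no grade, so it supports the inclusive test by analogy only. The no-other-cause condition, with its counterpart under Not related, is therefore the outlier. No sentence ranks the tests.

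**What the grade does not touch.**

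- AEs are recorded whatever their causality (7.2.1), so total and Grade 3–4 counts are unaffected.
- Investigators report all SAEs regardless of relatedness (9.5.1) and follow them all to resolution or stabilisation (9.5.2).
- The dose hold in 4.2 has its own, wider trigger, which also covers events thought possibly related.
- Wound sites are assessed every 4 weeks to Day 365 whatever the grade (4.2), and AEs are reviewed at those visits (section 8). The follow-up rule in 9.4.2 therefore adds little for local AEs.

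**The case against.** The strongest reply is that this is loose drafting whose intent can be recovered. Only the last sentence of Related gives an instruction, and the sentence before it may simply describe a typical related event. A reconciling reading also exists: a cause that explains an event could mean one that accounts for it fully. An AE to which the drug contributed would then not be explained by the other factor, and all the clauses would fit together.

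Both points stand as evidence of what was meant. They do not remove the problem, because the text neither ranks the sentences nor says that 'explain' means fully account for. The Not related bullet repeats the alternative-cause idea, so an investigator who applies the exclusive test is not misreading the page.

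The reply is also right that the stakes are limited. The study tests no formal hypotheses (11.2), and the affected outputs are descriptive.

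A reader might infer that the lead-in, the last sentence of Related and 9.2.2 each say outright that an AE is Related even when another cause is present. None does. The lead-in implies it by allowing for contribution, the last sentence is silent on other causes, and 9.2.2 has a different purpose.

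**Conclusion.** The conflict is real and narrow. For an AE with evidence of drug causality and another possible explanatory cause, 9.3.1 supports both grades. The consequence is possible under-counting and inconsistent grading in the treatment-related AE endpoint and its table. The follow-up-to-resolution rule for non-serious AEs is also affected, mainly for events away from the wound sites.

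No effect size can be derived, because the documents give no rate at which investigators would attribute an AE to another cause. The conclusion rests on the literal wording and on there being no statement of precedence.

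A reader might infer that local reactions in this trial will be misgraded, and might try to size the problem from Phase 1 injection-site rates. The documents do not support either step. Those rates would count events to be graded, not events graded wrongly. Phase 1 also used sutured incisions, and its edema and erythema were still called drug-related (2.3.1). The causality definition used in Phase 1 is not given, so that experience settles nothing in either direction.

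The point is worth correcting because the definition underlies a named safety endpoint and the correction is nearly free.

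**What to change.** In 9.3.1:

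1. Delete the second half of the first quoted Related sentence, which requires that no other cause explain the event.
2. Define Related by the section's own lead-in: a reasonable possibility that the investigational product caused the AE or contributed to it. Keep the term 'investigational product'; naming MRG-201 is unnecessary.
3. Limit the alternative-cause clause in Not related to AEs for which there is no reasonable possibility of a contribution from the investigational product.

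The cost is a wording change and matching eCRF guidance. It needs no new data, visits or analyses. The downside is that the related-AE count may be somewhat higher.

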### 9.3.2 Severity

All adverse events entered into the eCRF will be graded for severity using the NCI CTCAE, version 5.0. If an adverse event is not listed in the CTCAE version 5.0, then the Investigator will use the terms: Mild, Moderate, Severe, Life-threatening, or Death to describe the maximum intensity of the adverse event. For purposes of consistency, these intensity grades are defined as follows:

Severity	Definition
Grade 0	No change from Normal or Reference Range
Grade 1 (Mild)	No limitation of usual activities.
Grade 2 (Moderate)	Some limitation of usual activities.
Grade 3 (Severe)	Inability to carry out usual activities.
Grade 4 (Life-threatening)	Immediate risk of death.
Grade 5 (Death)	Resulting in death.

## 9.4 Collection and Reporting of Adverse Events

### 9.4.1 Initial Reporting of Adverse Events

Subjects will be evaluated and questioned generally to identify adverse events during the course of the study. Any events occurring prior to administration of the first dose of study treatment will be recorded on the Medical History eCRF. Events occurring after administration of the first dose of study treatment or those that increase in severity or frequency will be recorded as treatment-emergent AEs on the Adverse Event eCRF. Adverse events that occur up to and including 30 days after administration of the last dose of study treatment must be reported.

All AEs spontaneously reported by the participant and/or in response to an open question from study personnel or revealed by observation, physical examination, or other diagnostic procedures will be recorded on the Adverse Event eCRF. Any clinically relevant deterioration in laboratory assessments or other clinical findings, as assessed by the Investigator, is considered an AE and

must be recorded on the Adverse Event eCRF. In addition, an abnormal test finding will be classified as an adverse event if one or more of the following criteria are met:

- The test finding is accompanied by clinically significant symptoms.
- The test finding necessitates additional diagnostic evaluation(s) or medical/surgical intervention; including additional concomitant drug treatment or other therapy. Note: simply repeating a test finding, in the absence of any of the other listed criteria, does not constitute an AE.
- The test finding leads to a change in study treatment dosing or discontinuation of subject participation in the clinical research study.
- The test finding is considered an AE by the Investigator.

Wherever possible, a specific disease or syndrome rather than individual associated signs and symptoms should be identified. However, if an observed or reported sign or symptom is not associated with a documented disease or syndrome, the sign or symptom should be recorded as a separate AE. Laboratory data are to be collected as stipulated in this protocol. Clinical syndromes associated with laboratory abnormalities are to be recorded as appropriate (e.g., diabetes mellitus rather than hyperglycemia).

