#### **4.2 Treatments Administered**

Following completion of the punch biopsies on Day 1, one punch biopsy wound site will be treated with MRG-201 and the other wound site will be treated with placebo. The treatment for each wound site will be randomized (left versus right) and blinded but consistent throughout dosing. MRG-201 and placebo will each be administered as four 20- $\mu$ L injections around one wound site, with subjects receiving approximately 5.3 mg of the MRG-201 active moiety on each dosing day (approximately 1.3 mg per 20- $\mu$ L injection). After all Day 1 assessments and procedures are complete, subjects will be discharged to home.

Subjects will return to the clinic on Days 3, 5, 8, 10, and 12 to receive repeat injections with the same blinded study treatment that was administered at each wound site on Day 1. Subjects will return to the clinic on Day 19 for additional assessments and safety monitoring, and the Principal Investigator (PI) will determine whether any tolerability concerns are present and warrant consultation and safety data review with the sponsor's Medical Monitor. If at any point clinically significant safety or tolerability issues are observed by the investigator and are thought to be possibly related or related to MRG-201, the subject will not receive further administration of MRG-201 pending follow-up with the Medical Monitor. In this event, the investigator must notify the sponsor's Medical Monitor by email or phone within 24 hours, and a meeting with the sponsor Medical Monitor may be convened.

On Day 8, Day 12, Day 19, Day 29 (4 weeks  $\pm$  3 days after completion of the punch biopsies) and then every 4 weeks for 1 year (Days 57, 85, 113, 141, 169, 197, 225, 253, 281, 309, 337, 365, each  $\pm$  7 days), excisional wound sites will be assessed for keloid formation, photographic evaluations, and other study assessments.

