### **7.1 Clinical Assessments**

#### **7.1.1 Medical History**

Medical history will be recorded at screening. Any ongoing conditions and signs and symptoms observed prior to first dose of study treatment should be recorded as medical history.

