## **7.2 Safety Assessments**

### **7.2.1 Adverse Events**

AEs will be assessed at each study visit by direct observation and subject interviews. The severity of AEs will be evaluated using the NCI CTCAE, version 5.0. All AEs that occur from initiation of study treatment through 30 days after the last dose of study treatment must be recorded, regardless of causal assessment to study treatment.

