### **8.2.1 Day 1 (First Day of Study Treatment Administration)**

- Complete DLQI
- Verify inclusion/exclusion criteria.
- Obtain vital signs (blood pressure, heart rate, respiratory rate, and body temperature).
- Perform a complete physical examination.
- Collect blood for the following:
  - Hematology (predose; only if screening measurement was performed > 3 days before Day 1);
  - Clinical chemistry (predose; only if screening measurement was performed > 3 days before Day 1);
  - Antibody analysis;
  - PK (1 hour [ $\pm$  10 minutes], 2 hours [ $\pm$  15 minutes], and 3 hours [ $\pm$  15 minutes] postdose).
- Collect urine (predose) for urinalysis (only if screening measurement was performed > 3 days before Day 1) and pregnancy test (females).
- Perform a single 12-lead ECG (predose).

- Obtain two 6-mm punch biopsies and suture the resulting excisional wounds.
- Photograph biopsy sites (post-biopsy and suture).
- Administer intradermal study treatments.
- Review and record AEs and concomitant medications.

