### **11.3.1 Full Analyses Set (FAS)**

The FAS will include all randomized patients who received any amount of study drug (MRG-201 or placebo). The treatment assignment for FAS will be as randomized for efficacy analyses and actual for safety analyses. The FAS will be used for all efficacy and safety analyses. All patient data listings will use the FAS.

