Abbreviations: AE = adverse event; aPTT = activated partial thromboplastin time; ECG = electrocardiogram; eCRF = electronic case report form; FSH = follicle-stimulating hormone; HIV = human immunodeficiency virus; INR = international normalized ratio; PK = pharmacokinetic(s); PT = prothrombin time; SAE = serious adverse event

- a) Day 1 refers to the first dosing day for the first double-blind active treatment period.
- b) Complete physical examination at screening and Day 1; brief physical examination at all other time points.
- c) Only for women who are not surgically sterile as confirmation of menopause.
- d) Serum pregnancy test at screening and urine pregnancy tests on Days 1, 12, 29, 85 and at the end of the study for female subjects.
- e) Performed at screening, predose on Day 1, on Day 2 (approximately 24 hours after Day 1 dosing), and predose on Day 12.
- f) Hematology, clinical chemistry, and urinalysis (including microscopy) will be collected predose as indicated in the protocol. Laboratory assessments do not need to be performed on Day 1 if screening laboratory measurements were performed within 3 days prior to Day 1.
- g) 6-mm punch biopsy to create two excisional wounds (one treated with MRG-201 and one treated with placebo on Day 1) as described in the Study Manual.
- h) Subjects will receive intradermal injections of MRG-201 and intradermal injections of placebo at each time point. Refer to the Study Manual for detailed instructions on intradermal injections – Biopsy Site Selection, Injection, and Brief Photography Instructions.
- i) All AEs, including SAEs, will be recorded from the time of administration of the first dose of study treatment on Day 1 until 30 days after the last dose of study treatment or the end of study visit, whichever occurs last. Treatment-related AEs ongoing at the follow-up visit should be followed to resolution or until the investigator considers them “chronic” or “stable.”
- j) All medications (including over-the-counter medicines, herbal treatments, supplements, and vitamins) administered 30 days before the first administration of study treatment (Day 1) until the end of study (Day 365) will be recorded on the eCRF.
- k) On Day 1 and Day 12, plasma for PK will be drawn at 1 hour ( $\pm$  10 minutes), 2 hours ( $\pm$  15 minutes), and 3 hours ( $\pm$  15 minutes) after injection.
- l) On Day 2 and Day 13, plasma for PK will be drawn 24 ( $\pm$  4) hours after Day 1/12 dosing.

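### Biopsy harms that start before the first Day 1 injection and do not worsen are recorded as medical history, SAE coverage of that interval is contradictory, and biopsied but undosed subjects appear in no planned safety output

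*Combined protocol and SAP*

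**What the plan says.** **Order on Day 1.** Section 4.2 places dosing after the biopsies: "Following completion of the punch biopsies on Day 1, one punch biopsy wound site will be treated with MRG-201". The Day 1 list in Section 8.2.1 has the same order, with "Obtain two 6-mm punch biopsies and suture the resulting excisional wounds" ahead of photography and the injections. Section 8.4.1 repeats it for the 12-dose regimen.

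**Start of AE recording.** Section 7.2.1: "All AEs that occur from initiation of study treatment through 30 days after the last dose of study treatment must be recorded". Footnote i of Appendix A, repeated as footnote i of Appendix C: "All AEs, including SAEs, will be recorded from the time of administration of the first dose of study treatment on Day 1".

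**Events before the first dose.** Section 9.4.1: "Any events occurring prior to administration of the first dose of study treatment will be recorded on the Medical History eCRF". Section 7.1.1 agrees: "Any ongoing conditions and signs and symptoms observed prior to first dose of study treatment should be recorded as medical history". Section 9.4.1 then sets the boundary on the other side: "Events occurring after administration of the first dose of study treatment or those that increase in severity or frequency will be recorded as treatment-emergent AEs".

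**SAE reporting.** Section 9.5.1 gives an end to the reporting period but no start. It requires every SAE to be reported within 24 hours, whatever its cause.

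**Safety population.** Section 11.3.1 defines the Full Analysis Set (FAS): "The FAS will include all randomized patients who received any amount of study drug (MRG-201 or placebo". The same section uses the FAS for all safety analyses and all patient listings.

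**The concern.** The biopsies are done for the study. They leave two sutured 6-mm wounds in people chosen because wounds in that area are likely to form keloids. Immediate harms from them belong in the trial's safety record. The recording rules key on the first injection, however, and the biopsies come before it.

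Three things are at stake:

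- Some procedure harms would carry no required grade or causality judgement and would be missing from the AE tables.
- Sites would have conflicting instructions on whether a serious event in this interval is reportable within 24 hours.
- If a biopsy complication prevented dosing, that subject would appear in no planned safety output, although this is the case in which the harm mattered most.

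Section 10 provides for no study committee and Section 9.8 for no formal stopping rules. Oversight therefore rests on the Medical Monitor's review of the safety data, so it matters what those data include.

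**Working it through.** There is no stated figure to reproduce. The check is to follow events through the rules, and then to count the exposure.

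1. **The interval.** Sections 4.2, 8.2.1 and 8.4.1 all place biopsy and suturing before the first injection. An interval before dosing therefore exists for every subject. The documents give no length for it.

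2. **Onset in the interval, no worsening.** Sections 7.1.1 and 9.4.1 both send the event to medical history, and neither excepts study procedures. Section 9.3.2 requires grading of AEs entered in the eCRF, Section 9.3.1 requires causality for AEs, and Section 11.4.3.1 tabulates AEs. An event held as medical history meets none of these requirements.

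3. **Onset in the interval, later worsening.** Under Section 9.4.1 an increase in severity or frequency makes it a treatment-emergent AE. It is captured.

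4. **Onset after the first dose.** It is an AE under Sections 7.2.1 and 9.4.1, whatever its cause. A wound infection or delayed bleed at a biopsy site is captured. (These examples are illustrations. The documents list no biopsy complications.)

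5. **A serious event in the interval.** Section 9.5.1, read alone, covers it, because any SAE is reportable and no start is set. Footnote i of Appendices A and C, read alone, does not, because it starts recording of SAEs at the first dose. Section 9.2.4 defines an SAE as a kind of AE or suspected adverse reaction, and Section 9.4.1 does not treat pre-dose events as AEs, which adds to the doubt. Section 9.6 does not settle it: it covers only events attributed to the investigational product.

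6. **A subject biopsied but not dosed.** FAS membership requires a dose. Safety analyses and listings all use the FAS, so this subject is in none of them.

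7. **Appendix B.** The AE rule there is footnote h. That schedule covers the second dosing cycle, and Section 7.4.1 places the biopsies only on Day 1 of the first cycle. The problem does not arise there.

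8. **Exposure.** Biopsies = 2 × subjects.
   - Planned first cohort: 2 × 12 = 24.
   - Cohort at its ceiling: 2 × 16 = 32.
   - All six cohorts at the ceiling: 6 × 16 = 96 subjects, and 2 × 96 = 192 biopsies.

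   No complication rate is given, so these counts cannot be turned into a number of missed events.

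**The case against.** The strongest reply is that the gap is narrow and little is lost. Much of this stands.

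- **A reader might infer that biopsy harms in general drop out of the safety data.** They do not. Anything that starts or worsens after the first dose goes on the AE form. Only non-worsening events with onset before the first injection are affected.
- **A reader might infer that SAEs in this interval are excluded from reporting by rule.** The documents do not establish that. Section 9.5.1 is the operative SAE section and its duty is broad, and a schedule footnote on recording does not plainly override it. Equally, a site working from the schedule could reasonably conclude that nothing is due. The supportable statement is that the passages contradict each other.
- **The information is not destroyed.** It is on an eCRF, Section 12.2 requires an eCRF for everyone who consents, and Section 6.3 captures medication from 30 days before dosing. The Medical History form is not shown and might collect more than the protocol requires. Even so, the protocol does not require grade or causality for these events, and no planned output shows them for an undosed subject.
- **The comparison of MRG-201 with placebo is not obviously biased.** Both wounds in each subject are made in the same way. The point concerns completeness of safety capture.
- **The figure of 192 might be taken as a count of missed events.** It is a ceiling on biopsies performed, and it assumes that all five optional cohorts fill completely.

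**Conclusion.** The concern holds in a limited form. Non-worsening biopsy harms with onset between the first punch and the first injection are classified as medical history and so fall outside AE grading, causality assessment and the AE tables. SAE coverage of the same interval is contradictory between Section 9.5.1 and footnote i of Appendices A and C. A subject biopsied but never dosed is in no planned safety table or listing.

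The size in events is unknown. It depends on an immediate complication rate and an interval length that the documents do not give, and on how often a biopsied subject would go undosed, which they also do not state. The conclusion assumes that sites apply Sections 7.1.1 and 9.4.1 as written and that no form or manual outside these documents says otherwise. It is worth correcting despite the narrow window, because a stated rule misclassifies harms from a research procedure and the remedy is cheap.

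**What to change.** 1. In Sections 7.1.1, 7.2.1 and 9.4.1, and in footnote i of Appendices A and C, start AE recording at the beginning of the first Day 1 biopsy. Leave Appendix B alone.
2. Reconcile Section 9.5.1 with footnote i by stating one SAE start, no later than that biopsy.
3. Add a study-procedure option to the causality assessment in Section 9.3.1, which at present offers only relatedness to study therapy.
4. Flag events with onset before the first injection as pre-treatment, and keep the treatment-emergent definition at first dose. The planned treatment-emergent summaries then do not change.
5. Add a listing of pre-treatment procedure events for all biopsied subjects, including any not dosed, as a stated exception to the FAS rule for listings in Section 11.3.1.

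The cost is protocol wording, one causality option and one flag on the eCRF, and one listing. The downside is a few more minor procedure events for sites to record.
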